relationships, family economic resources, and hypertension at 12 and 18 years postpartum. H9: NV effects on offspring outcomes (H1-6) will be mediated, in part, by NV effects on prenatal health behaviors, preterm delivery, PIH, breast feeding, screen time at age 12, improved partner relationships, family economic resources through age 18, and obesity and prehypertension at ages 12 and 18. Tests of mediation will follow the empirical and theoretical model shown in Figures 1 and 2. We will employ mediation analyses using structural equation models to examine causal processes, including the direct and indirect effects of treatment on outcomes.^{100,101} To illustrate, we have hypothesized that NV will have an indirect effect on maternal arterial stiffness through its effect on PIH, preterm delivery, and the count of short inter-pregnancy intervals. To test one aspect of this hypothesis, we will regress maternal arterial stiffness on the count of closely spaced subsequent children (child density) within the control group; we also will regress child density on the treatment contrast. If the paths from the control sample to child density and from density to arterial stiffness are both significant, we will have met the joint significance test criterion. We will next calculate the indirect effect, based on these same two path coefficients, and compare the resultant z' to Mackinnon's table of critical values. If the z' is equal to or higher than the appropriate critical value, we will conclude that density of subsequent children mediates the effect of nurse visitation on maternal arterial stiffness. We will use this approach for each hypothesized mediator separately and jointly to develop a map of mediation.

Challenges in the Conduct of This Work

Missing Data. Missing data in this trial have been remarkably low. We are sensitive to the potential pitfalls of analyzing only cases with complete data.¹⁰⁵ We have complete data on all relevant background characteristics, which we will examine to address potential attrition bias. We also will compare our analyses to the same analyses employing inverse proportional weighting. We will perform sensitivity analyses to ensure that results are similar under various assumptions. We will determine whether imputation is valid and has sufficient added value with our data to justify the complexity involved in reporting these analyses.

Increased Difficulty in Tracing and Engaging Participants. The most significant challenge to this work is attrition bias. While this problem is minimized for the mortality outcome, it is a challenge for those that depend on direct assessments. The best solution is to invest sufficient resources into locating and engaging participants. Note that this study: 1) employs the same local study leader (the wife of a local minister) who will continue to engage the sample; 2) refers participants for further evaluation and treatment for health problems; and 3) remunerates participants adequately for travel and time. These factors reduce participant attrition.

Conducting Assessments among those Outside of the Memphis Region. We have chosen measures that, for the most part, can be assessed in both home and office, except for body fat and arterial stiffness, which creates possible cross-context challenges with validity and reliability, which we will examine as part of this study.

Multiple Comparisons. If we were to make Bonferroni-like adjustments to our statistical tests in this study, the cost of conducting such studies with adequate power would be prohibitive, given the large number of outcomes examined over time. Our approach has been to make specific hypotheses for primary outcomes, look for coherence across outcomes, and to emphasize the importance of replication.¹⁰⁶ This is a sensible strategy that in the long-run minimizes costs and accelerates scientific discovery.

IV. RISK/BENEFIT ASSESSMENT

1. Risk Category. Minimal risk.

Potential Risk. Risk to participants for this study are expected to be minimal; these minimal risks will be minimized by using appropriate space and equipment, attending to all protocols/procedures, and providing adequate personnel selection, training, and supervision. The collection of questionnaire data has inherent risk to confidentiality, however prior to and during study implementation study personnel will be trained to follow protocols to minimize that risk. All study personnel will follow HIPAA regulations and be trained and certified in Human Subjects Protections by the relevant university or institution. We expect that most study activities will pose little discomfort or risk to subjects. If needed, this study will be able to refer to local support services. A blood draw is planned. In no instance will we collect more than

the allowable volume of blood (50 ml), based on consideration of body weight. Risks from blood draws are minimal and may include fainting, dizziness, ill feeling, and bruising during and/or after the blood draw and there is a low risk of infection. To minimize the risk trained nurses/phlebotomists will perform blood draws while participants are sitting or lying down. Collection of urine samples is done as a part of the standard of care and is not likely to cause distress. Measurement of weight and blood pressure is done as part of the standard of care and is not likely to cause distress. Bioelectrical impedance analysis is similar to standing on a scale and not likely to elicit additional distress beyond what weight measurement might. SphygmoCor EXCEL is not likely to elicit additional distress as it is a painless procedure. Anthropometric measurements of obese individuals may cause mild distress. To minimize this distress, the proposed assessments will be detailed during the consent process and confidentiality will be assured. Information will be provided to participants regarding the handling and the identification process involved with the data. Information that identifies subjects and subject number will be kept in the secure servers. Only study staff who have contact with participants will have access to this information. Note that the safety of the Tanita Body-Composition analyzer has not been established for pregnant women, so women who are pregnant or may be pregnant will not have this procedure conducted.

The potential risks to the participants involve the breach of confidentiality. To the extent that the data gathered are divulged to those who are not involved in the data gathering and processing, the subjects are at risk for a breach of their confidentiality. The potential for this problem is reduced by the use of identification codes rather than names on the data collection forms, keeping the data and consent forms in locked file cabinets, and instituting procedures whereby breach of confidentiality by the data gathering and clerical staff is grounds for immediate termination. Individuals with access to the research data are the study staff located at the Memphis site, data management staff based in Rochester, NY, and the Colorado and Rochester-based programming and analysis staff, along with study PIs. All computers will be password protected. Data files will be encrypted during transfer between organizations (e.g. Rochester and Colorado) and stored on servers only accessible to those mentioned above and who have undergone Human Subjects Training. Note that the Tanita body-composition analysis will not be conducted with pregnant women or women who may be pregnant.

Respondent Boredom/Fatigue. The time for data- collection may seem long to some participants. Based on our experience at the 18 year follow-up, total expected time required for the assessment is approximately 2.5 hours which will be acceptable to participants given that prior follow-up assessments have been of comparable length. Nevertheless, some participants may experience boredom or fatigue.

Abnormal BP measurements may indicate a serious health problem.

Protection against Risks. Risks to the participants will be fully explained during the informed consent process and repeated as needed during data collection activities. All study personnel will undergo extensive, standardized training and certification with ongoing quality control monitoring. We will adhere to strict data storage and confidentiality procedures to ensure the privacy and confidentiality of the participants. Only trained phlebotomists/nurses will collect blood samples and only trained study team members will have contact with the subjects. To address concerns about psychological issues (including anxiety and depression), all individuals will be informed about mental health services that are available and will be encouraged to discuss concerns that they may have with their mental health with their clinicians. Wherever possible, the study will make use of existing resources. Interviewers/researchers will be familiar with clinic resources and will be trained in the administration of the questionnaire measures. If patients are highly distressed or show signs of serious depression or psychiatric illness during the study, they will be referred for help through their local county mental health services. Disclosure of child abuse or neglect revealed during the study or observed by study staff will be referred to Child Protective Services in the county in which the child (or parent) lives. Reporting of child abuse or neglect may have psychological and legal ramifications for the family; we will manage any potential disclosures in cooperation with local child welfare services. If an individual reports being

a victim of domestic violence, they will be referred to domestic violence services in the county in which they live. If study staff is concerned about any information shared by a prisoner participant regarding the possibility of self-harm or harm to others, study staff will inform the prison warden or his/her designee via telephone call and will document this call.

Boredom/fatigue risk. This risk will be reduced by: 1) respecting participants' time and contribution; 2) creating a comfortable, welcoming environment; 3) providing a clear explanation of procedures and length of time required during the recruitment, scheduling, and consenting processes; 4) providing transportation and remuneration to participants to reduce associated stress; 5) varying the activities within the assessment; 6) providing a break/refreshment time in the middle of the session; and 7) offering the opportunity for additional breaks or terminating the assessment.

If the blood pressure readings are abnormally high, defined as average systolic BP (SBP) readings greater than or equal to 180 mmHg and/or an average diastolic (DBP) readings greater than or equal to 110 mmHg), participants will have their blood pressure re-checked and assessed by a RN. Participants will be provided with a handout indicating their blood pressure measurements and advised to follow up with their primary care provider or the emergency department as soon as possible. If the subject does not have a primary care provider a referral will be provided.

2. **Potential Benefits to the Subjects.** The participants themselves will receive no direct benefit from this study, although those with potential health problems identified during the course of the assessment will be encouraged to seek further evaluation and treatment through existing health and human services in their community.

Confidentiality of Data and Computer Records for all Coordinating Sites. It is important to note that this study will be conducted in collaboration with the University of Rochester (FWA00009386), and the Medpace Reference Laboratories; and, directly obtained participant data will be collected under the oversight of University of Rochester investigators in a Project controlled office in Memphis, Tennessee. The Medpace Reference Laboratories will not have access to individual identifiers. In all sites, staff given access to the data will have all human subjects training up to date and have read and agreed to everything in the confidentiality agreement. A log will be kept of any staff granted access to the data. We will take the following steps to protect the confidentiality of our data and computer records:

- All study staff will receive extensive training in maintaining participant confidentiality.
- Identification codes rather than names will be used on all data collection forms and data transfers.
- The handling of data generally will be limited to the numerical values and statistical summaries.
- The identifiers linking identification codes with individual names are only available to the Memphis staff, Rochester staff and PI and co-PIs. They will be kept in a secure database on an encrypted server.

< PHI is stored in File Maker Pro 18 which is maintained by the University of Rochester School of Nursing. This same software has been used to store participants PHI for past phases of the Memphis New Mothers Study. FileMaker Pro: University of Rochester, School of Nursing runs a FileMaker Pro (FMP) 18 server that is used for protecting Protected Health Information (PHI) (including name, phone number, email address, home address, and Social Security Number (SSN)). This database will hold the link between participant ID and actual identity and is designed to ensure that authorized users have minimal data access as possible in their roles.

- Only those who need to assess PHI information will have access granted by their login name privilege set. Usernames and passwords are managed by Rochester study office and a list of usernames and allowable PHI access will be obtained on a log in Rochester study office.
- The FileMaker server is housed in the UR Medical Center's internal network, which is protected from the public Internet by firewalls, along with the UR Medical Center's electronic

health record and other restricted assets. The server runs Cylance anti-virus and is backed up nightly with 30 days' retention with replication to a off-site facility.

- Consents and any data collection forms that are in paper format will be stored in a locked file drawer, in a room that is locked when it is unoccupied.
- Data collection forms will be shredded when they are no longer relevant (e.g., after entered into REDCap).
- To ensure that data are not co-mingled with data from other projects, data will be stored in its own subdirectory with access only granted to individuals approved to work on this project.
- The data received will not be used for purposes other than what is described in this application, or consented to for future research by study participants.
 - Personal computers will be logged off at the end of each work day to prevent inadvertent access to the network and to data stored on the computer hard drive.
 - A screensaver password will be engaged during the day to prevent people from accessing data while individuals are out of the office.
 - An access control list through arrangements with network administrators will be used to limit the number of people who have permission to access the network subdirectory where sensitive data are stored.
 - Consideration may be given to storing sensitive data only on the secure network when it is being analyzed. More permanent storage would then be on an encrypted drive on a server at the University of Rochester. .
 - Sending sensitive data via email will be minimized.
 - Email within the University of Rochester and University of Colorado is automatically encrypted
 - All data transfers will be done via Box (from Memphis to UR; from UR to Colorado; from Medpace to UR). See flow chart at end of document.
- Confidentiality of Data and Computer Records Specific to Denver
 - < Physical Control. Paper associated with study PHI will be stored in a locked cabinet in our locked file room which is accessible to a very limited number of people who must use their ID badge to electronically unlock the door. During non-work hours the building itself is locked and an ID badge is required for admittance. All output that is identifiable will be recycled using a protocol for sensitive data (i.e. put in a locked trash container in a secure room and ultimately shredded by a company that deals with sensitive data).
 - < Technical Control. Data will be stored on the University of Colorado network on a drive called "Sensitive" which has very limited access (i.e. one statistician and the data coordinator). Programs and output will be on the same "Sensitive" shared drive. No identifiable data will be stored outside of this Sensitive drive.
 - < Administrative control. As part of the university network the Office of Information Technology provides an enterprise level backup service for backup of data. Data on the server are backed up the night the file is first created; As the file is modified, each revision of that file is also backed up and is kept for 30 days; At day 31, the earliest revision is removed from the backup environment; The last copy of the file is kept (assuming no additional modifications) until it is deleted from the server; Secondary of backup data is retained off-site for disaster recovery purposes.
- Confidentiality of Data Specific to University of Rochester, the Memphis Study Office, and the Medpace Reference Laboratories. The use of the following modalities ensures secure transfer of data between Memphis where the data are gathered and University of Rochester where the data are processed and stored and the finished file sent to University of Colorado.
 - < University of Rochester School of Nursing's Windows File Server – This is the site where information private to Memphis/SON will be stored. Connection to it from a non-direct site requires use of the University of Rochester Medical Center (URMC) VPN (Cisco AnyConnect, which requires Duo multi-factor authentication). This server is in the University of Rochester's

Primary Data Center, which provides adequate physical security controls to meet its Electronic Medical Record requirements.

- < Memphis Computers — All of the desktop and laptop PCs will be secured to meet URMC standards: managed full disk encryption (Microsoft BitLocker) plus anti-virus (Cylance).
- < Memphis Network — We have a permanent VPN in place between the Memphis network and the URMC network to protect data in motion.
- REDCap — The University of Rochester manages a REDCap database instance. Access to the site requires HTTPS / TLS transport security. This service is also hosted in the University of Rochester's Primary Data Center.
- Box — University of Rochester has a HIPAA BAA with Box for storage of data and sharing with collaborating institutions / researchers. This is the University of Rochester's preferred method of transporting data electronically. Box is the primary place where information is to be shared, between Memphis (Rochester employees), University of Rochester, MedPace, and University of Colorado. Box protects the data during transmission by HTTPS / TLS security. Strict, streamlined procedures will be followed regarding data transmission and its confirmation.
 - Memphis staff will upload data into Box at the end of each data collection day and send confirmation to Rochester staff on identification codes uploaded. Rochester staff will be responsible for confirming receipt of data by identification codes and the transfer of data from Box to the University of Rochester file server. All files will be removed from Box once files transfer is complete. A similar process was in place at the 18 year follow up between the Memphis office and the University of Rochester.
 - Memphis staff will ship blood and urine samples to the Medpace Reference Laboratories labeled by an identification number that is different from the main study identification number used in data collection. MedPace staff will transfer blood and urine results to the University of Rochester in Box. Rochester staff will be responsible for confirming receipt of data by identification codes and the transfer of data from Box to the University of Rochester file server. All files will be removed from Box once file transfers are complete.
 - University of Rochester will upload the final analysis file via Box to the University of Colorado using the same process.
 - University of Rochester Box will have separate shares with the Memphis office, Medpace Reference Laboratories, and University of Colorado with separate permissions.

Data and Safety Monitoring Plan

Monitoring: We have created an independent Data Safety Monitoring Board (DSMB) consisting of [name]., Professor of Pediatrics at the University of Colorado, [name], biostatistician from The Children's Hospital Research Institute in Denver, and [name]. MPA, instructor, Department of Family Medicine, and chair of the DSMB. This group will meet as needed (and at least yearly) to review any reports of untoward events and to monitor their resolution. At the stage of analysis and interpretation of data from the next phase of follow-up, this group will meet with the principal investigators and members of our biostatistical team to review the findings to determine whether there are any negative side effects. Minutes will be kept of the meeting and following DSMB meetings, the results of the meeting concerning possible negative side effects will be documented by [name] and sent to the PIs and appropriate NIH staff, or other appropriate institutions depending upon the nature of risk identified.

Management of Untoward Events

How an "Untoward Effect" May Be Discovered:

- Data analysis uncovers treatment effects with higher rates of adverse events or outcomes in the nurse-visited groups compared to the control groups. While statistically significant differences may not pose a problem for individuals, the possibility of adverse program effects needs to be considered carefully.
- Staff member discovers that participant personal health information has been revealed to individual or group who does not have permission for this information.

- Participant verbalizes or displays high level anxiety or fear to the interviewer or other staff member regarding research procedures.

How an Untoward Effect Will Be Reported:

- At the stage of data analysis, data analysts and investigators will keep a log of any test of treatment contrasts that produce statistically significant effects in the unexpected direction, or a pattern of trends in the unexpected direction. The Data Safety Monitoring Board group will meet with the principal investigators and members of our biostatistical team to review the findings to determine whether there are any negative side effects. Following the DSMB meeting, the results of the meeting concerning possible negative side effects will be documented by [name] (a member of our Data-Safety Monitoring Board) and sent to the PIs, the IRB, and appropriate NIH staff.
- Any breach of confidentiality is cause for termination. Breaches of confidentiality will be identified and reported to the DSMB and IRB by the PI whenever they occur. The DSMB will report these infractions to the IRB and NIH.
- Instances of extreme anxiety or fear will be noted in a confidential log and reported to the PI, who in turn will report this information to the DSMB. A record of these problems will be submitted to the IRB. Referral of Cases for Further Evaluation and Treatment: Should an Untoward Event occur, the data gathering staff in Memphis will discuss the untoward event with their supervisor, who will make an appropriate referral for further evaluation and treatment within the health and human service delivery system in Memphis. The Memphis leadership staff members have been with the study for nearly 15 years and are well-positioned to evaluate and make appropriate community referrals, given the types of untoward effects that may occur in this study.

Follow-up and Referral: The PI will be informed of all reported adverse outcomes, including who is referred for further evaluation and treatment and the outcomes.

Confidentiality: The PI will maintain information on monitoring untoward events, but will do so without specific patient identifiers.

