Data Processing. Blood and urine samples will be processed for storage on site in Memphis, stored at -80 Celsius, and shipped weekly/bi-weekly to the Medpace Reference Laboratories, where the MedPace team will conduct standard assessments for the clinically relevant analytes as they are received. MedPace will only have unique codes which are not the same as study IDs and they will not have access to individual identifiers. They will send results to the University of Rochester as they are analyzed through Box; the UR team will be responsible for creating a work file for analysis and one of the RNs on the Rochester team will notify participants of the results of their clinically relevant blood and urine assays (e.g. lipid panel, HbA1c). Specimens for less commonly assayed analytes (those used for research purposes only - IL-6, TNF-alpha receptor 2, IGF-1) will be stored and assayed in batches.

All interview data will be entered into REDCap by study staff and/or study participants. Physical assessment data will be entered into REDCap by the Memphis study staff. These data will be accessed by UR data management staff for the construction of data files. Signed consents to review medical and/or hospitalization records will be sent to the UR data processing team where they will process requests for records. Upon receipt of medical records, the UR team will code lengths of stay and I-CD 10 diagnoses. Biomarker and assessment results will be interpreted in light of self-reported diagnoses, medications, and medical/hospitalization records. Original signed consents and releases will be forwarded to and stored in Denver.

Analysis

Approach to Addressing Specific Aim One

For Hypotheses 1-5, we will examine NV-C adjusted mean differences in the individual measures specified in each of the primary outcome domains, (as well as values that exceed clinical thresholds) employing statistical models described below in the Statistical Models and Methods section. For Hypothesis 6, we will employ survival analysis to examine differences.

H1: Measures of Obesity, Fat, and Fat Distribution. We will compare NV and C participants on standard measures of BMI, waist and hip circumference, as well as segmental fat mass in arms, trunk, legs, and total body. Note that for assessments conducted outside of the Memphis office, we will resort to % total body fat.

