The primary analyses will make use of general linear model methods and their extensions.⁸⁹⁻⁹⁴ The focus will be on (1) full model specification to account for all sources of variation, and full examination of interactions among model factors, including examination of homogeneity of regressions to understand interactions between classification effects and covariates; (2) generalized models to analyze dichotomous outcomes with binomial error distributions and count data assumed to have negative binomial distributions; (3) generalized linear mixed models (including repeated measures and growth-curve models) to account for correlated data and to examine differences in change over time; (4) semiparametric methods to model relations between variables without requiring a specific functional form;⁹⁵ (5) survival analyses including Kaplan-Meier, competing risks and Cox hazard models;⁹⁶⁻⁹⁹ (6) mediation analyses using structural equation models to examine causal processes, including the direct and indirect effects of treatment on outcomes.^{100,101}

The primary classification factors for examination in our models, as determined by our hypotheses and earlier work, include treatments (Control vs. Nurse Visited - T), maternal psychological resources (low versus high based on a median split – P), sex of offspring (S), and follow-up time (A) for outcomes assessed at multiple time points (e.g. obesity) – T|P|S and T|P|S|A. Covariates will be selected using a post-double-selection lasso (least absolute shrinkage and selection operator) procedure.¹⁰²⁻¹⁰⁴ This procedure will select covariates that are most related to intervention status (i.e. differences at randomization) or related to the dependent variable. Candidate covariates will include an index of household poverty, obesity, and maternal

pre-pregnancy BMI.

Statistical Power/Smallest Detectable Differences for Proposed Follow-Up

Given that sample size is fixed, we show below calculations of the smallest detectable treatment-control differences for the 29-year follow-up. Calculations for representative outcomes were carried out with the following assumptions: a Type I error of .05, Type II error of .20 (power of .80), 2-tailed tests, 10 percent of the variance accounted for by other terms in the model for normally distributed variables and N=600. Disproportionate sample sizes in Control and Nurse-Visited groups are taken into account.

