Hypotheses 1-6 (primary): The NV group is hypothesized to have: H1: lower measures of obesity, (BMI, waist to hip ratios, segmental and % body fat, visceral fat); H2: lower risks for macrovascular disease, reflected in measures of functional arterial stiffness (peripheral BP, cfPWV, AI); H3: fewer markers of CKD - higher eGFR and lower microalbumin/creatinine ratios; H4: better metabolic outcomes (lower levels of HbA1C, TC, HDL, LDLc, TG, AST/ALT ratio); H5: lower levels of immune/inflammatory markers (hsCRP, fibrinogen, IL-6, TNF-alpha receptor 2, IGF-1); and H6: lower mortality rates. We will test Hypotheses 1-5 by examining each of the primary outcomes listed above as dependent variables in our primary T|P|S model, plus covariates from the post-double-selection lasso results. Outcomes also measured at earlier time points will include an additional classification factor for first-born offspring age at assessment (A). We will examine treatment-control difference summing across levels of maternal psychological resources and sex. In addition, we will examine planned contrasts for males and females, and mothers of males and females. Outcomes for hypotheses 1-5 are normally distributed and will be examined in the general linear model or mixed linear model for repeated measure outcomes. Secondary analyses will examine some outcomes in their dichotomous form for those values that cross clinical thresholds (e.g., obesity), which will be analyzed in the logistic model or generalized linear mixed model for repeated measure outcomes.⁹⁰ Hypothesis 6, related to mortality 6, will be examined in survival analysis by treatment condition without additional classification factors consistent with our earlier report on mortality.^{99,69}

Hypotheses 7: NV effects on H1-5 outcomes will be greater for female offspring and mothers who gave birth to females. Planned contrasts in the above aforementioned models for all primary outcomes, with the exception of mortality (given low base rates), will focus on female offspring and mothers of females.

Hypothesis 8: NV effects on maternal outcomes (H1-6) will be mediated, in part, by NV effects on prenatal health behaviors, preterm delivery in first and subsequent births, and PIH in first births; closely spaced subsequent pregnancies, maternal sense of mastery, stable/supportive partnered

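### Three of the five H5 markers are assayed in batches, but the stated model has no batch term and the plan does not say how specimens are allocated to batches

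*Combined protocol and SAP*

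**What the plan says.** All references are to the combined protocol and SAP.

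- **Data Processing.** The laboratory will "conduct standard assessments for the clinically relevant analytes as they are received". The less common, research-only analytes (IL-6, TNF-alpha receptor 2 and IGF-1) are treated differently: their specimens "will be stored and assayed in batches". Samples carry codes that differ from the study IDs.
- **Tests of Hypotheses, Hypotheses 1-6.** H5 covers hsCRP, fibrinogen, IL-6, TNF-alpha receptor 2 and IGF-1, and is listed as primary. Each outcome is examined "in our primary T|P|S model, plus covariates from the post-double-selection lasso results".
- **Statistical Models and Methods of Analysis.** T, P and S are treatment, maternal psychological resources and sex of offspring. On the lasso: "Candidate covariates will include an index of household poverty, obesity, and maternal" pre-pregnancy BMI. The same section sets a general aim of "full model specification to account for all sources of variation".
- **Not stated anywhere.** How specimens are assigned to batches, how many batches there will be, the assay CVs, and whether batch is recorded or modelled.

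**The concern.** A batched immunoassay usually carries some between-run variation. If the model has no term for it, that variation goes into the residual and the treatment contrast for these markers is less precise than it need be. If, in addition, the nurse-visited share differs from batch to batch, part of the batch variation enters the contrast itself.

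The design has little slack: power is about 82% at its own stated detectable difference of 0.24 SD. The plan also makes no multiplicity adjustment and relies on coherence across outcomes. If the three assays share batches, one uneven allocation could push all three markers the same way, and that would look like coherence.

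**Working it through.** **1. The plan's own figure.** Inputs from the power section: two-sided alpha 0.05, power 0.80, 10% of variance explained by other model terms, N=600. The 514:228 allocation applied to 600 gives 415.6 and 184.4, assuming equal retention.

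Detectable effect = (1.960 + 0.842) × √0.90 × √(1/415.6 + 1/184.4) = 2.802 × 0.9487 × 0.0885 = 0.235, which the plan gives as 0.24. With N=300 the same formula gives 0.333, given as 0.33. Power at 0.24 is 81.6%. The plan's figures reproduce.

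**2. Batch share and loss of precision.** These CVs are assumptions; the documents give none. With arm unrelated to batch:

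share = CV_batch² / (CV_batch² + CV_person²); SE inflation = 1/√(1 − share) − 1.

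| Marker | CV_batch | CV_person | Share | SE inflation |
|---|---|---|---|---|
| TNF receptor 2, IGF-1 | 5% | 30% | 25/925 = 2.7% | 1.4% |
| TNF receptor 2, IGF-1 | 10% | 30% | 100/1000 = 10.0% | 5.4% |
| TNF receptor 2, IGF-1 | 10% | 25% | 100/725 = 13.8% | 7.7% |
| IL-6 | 5% | 70% | 25/4925 = 0.5% | 0.3% |
| IL-6 | 10% | 70% | 100/5000 = 2.0% | 1.0% |

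**3. The same loss as power.** In within-batch SD units, the detectable effect without a batch term is 0.2352/√(1 − share):

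| Batch share | Detectable effect | Power at 0.24 |
|---|---|---|
| 0% | 0.235 | 81.6% |
| 2% | 0.238 | 80.8% |
| 5% | 0.241 | 79.6% |
| 10% | 0.248 | 77.4% |
| 20% | 0.263 | 72.5% |

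The plan defines its effect size in pooled SD units, which would already contain any batch variance. Read that way, 0.24 stands, and a batch term would improve on it: at a 10% share, from 0.235 to 0.2352 × √(0.80/0.90) = 0.222.

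**4. Type I error.** I used a simulation of 600 people in 6 or 15 equal batches, with 3,000 replicates per setting. Near 5%, Monte Carlo error is about √(0.05 × 0.95/3000) = 0.4 points.

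- *Batches filled at random with respect to arm.* Type I error without a batch term is 4.4-5.1%, so it is not inflated. Power without and with the term is about 79-81% and 81% at a 5% share, 78-79% and 81-82% at 10%, and 72-74% and 79-81% at 20%.
- *Arm share varying further between batches.* The assumption is an SD of 0.3 on the logit scale. Around 228/742 = 30.7%, that is about 0.3 × 0.307 × 0.693 = 6.4 percentage points, on top of random variation. Type I error without the term is then 4.5-5.5% at a 5% share, 5.6-7.0% at 10% and 7.0-8.3% at 20%. With the term it is 4.4-5.2%.

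The batch shares, batch counts and the 0.3 are all assumptions.

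**The case against.** **The plan may already cover this.** It aims at "full model specification to account for all sources of variation", and its list of candidate covariates is open. That supports adding a batch term but does not specify one. A lasso can choose only among variables that are recorded and offered to it, and it may drop batch indicators even then.

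**Run layout belongs in a laboratory manual.** This is fair for the run list, and its absence here does not show that none was planned. It is less fair for the model term, which belongs in the analysis plan.

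**Masked staff and coded samples prevent sorting by arm.** They make deliberate sorting unlikely, and that stands. But a laboratory that does not know the arms cannot balance them across batches either.

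**The effect may be negligible.** For IL-6 it probably is. For the other two markers, the 7.7% needs the worst corner of both assumed ranges. At a 5% share or less, the power loss is about 2 points or less.

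Two stronger readings are tempting, and the documents support neither.

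- *A reader might infer that specimens are not balanced across batches, or that batches are filled in order of arrival.* The plan states neither. Weekly or two-weekly shipping does not fix the assay order of stored specimens.
- *A reader might infer from Table 2 that distance links arm to batch.* More nurse-visited than control mothers live over three hours away: 29/200 (14.5%) v 50/443 (11.3%), p about 0.25. Offspring run the other way: 30/214 (14.0%) v 79/473 (16.7%), p about 0.37. These are addresses already updated in 2018, not tracing order, and participants interviewed virtually have no in-office assessment. Even if every distant mother sat in batches shifted by two batch SDs, the contrast would move by only about 2 × 0.371 × 0.032 = 0.024 SD. Here 0.371 = √0.138, the batch SD in total-SD units in the worst corner above.

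**Conclusion.** The point holds as a cheap improvement. The plan names three batched primary markers, states no batch term for them, and leaves batch allocation unspecified. If the stated model is run, batch variation stays in the error term.

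With arm unrelated to batch, the cost is precision only: about 1.4-7.7% on the standard error for TNF receptor 2 and IGF-1, and 0.3-1% for IL-6, under the assumed CVs. Inflated type I error needs two further conditions together: arm shares that differ across batches by more than random filling gives, and a material batch variance, of the order of 10% or more in the simulation. The documents show neither. They establish a gap in specification; they do not establish bias, and the detectable effects of 0.24 and 0.33 SD are not in error.

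**What to change.** 1. Record the batch number for the IL-6, TNF-alpha receptor 2 and IGF-1 assays. Where runs are already complete, recover it from laboratory run records if these exist.
2. State in the analysis section that batch enters the models for these three markers as a fixed effect or, with many small batches, a random effect. It should be forced in and kept outside the lasso selection.
3. For specimens not yet run, have the data team give the laboratory a coded run list that randomises specimens to batches with the two arms in the same proportion in each. The laboratory stays masked.

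The cost is one run list and one factor in three models. With 6 or 15 batches, fixed effects use 5 or 14 degrees of freedom out of about 600. Specifying the term now also avoids a choice made after the data are seen.
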